3.8.3. Dose Adjustment for Non-Hematologic Toxicity

See [Table 4](#) Dose Adjustment Guideline for drug related non-hematologic toxicities based on worst grade.

Table 4 Dose Adjustment Guideline for Drug Related Non-Hematologic Toxicity

Worst Grade	Dose Adjustment
G1	No change in dose
G2	Continue dosing with no change OR Consider holding for up to 2 weeks for toxicity to resolve to baseline or \leq Grade 1, then continue at the same dose OR dose reduce to 1 dose level lower per dose escalation scheme if the toxicity is considered a DLT.
G3 and 4	Hold for up to 2 weeks for toxicity to resolve to baseline or \leq Grade 1, then dose reduce to 1 dose level lower per dose escalation scheme If no recovery to \leq Grade 1* or baseline after 14 days, patient should be withdrawn.

If the non-hematologic toxicity or event resolves to baseline or \leq Grade 1 within 14 days of stopping therapy, treatment with GSK2816126 may be restarted at 1 dose level lower than the current dose. For a non-DLT, the treatment with GSK2816126 could restart at a full dose, if deemed appropriate.

If the non-hematologic toxicity does not resolve to \leq Grade 1 or baseline within 14 days, the subject should be withdrawn from the treatment permanently (Section 6.3). However, if the investigator and GSK Medical Monitor agree that further treatment will benefit the subject, treatment can restart at 1 dose level lower and under weekly clinical monitoring. If the toxicity resolves to \leq Grade 1 or baseline, the dose may be resumed to the initial dose level.

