	to 3000 mg/day, however, only a limited number of subjects have received GSK2816126.	clothing with long sleeves, sunglasses, and broad rim hat that protect the skin from sun exposure AND use a broad spectrum sunscreen (e.g., UVA and UVB protective with minimum SPF 30) on any uncovered areas of the body if outdoors from the time of first dose of study medication until at least 2 weeks (14 days) following last dose of study medication due to long elimination phase.
Hepatic Toxicity	
In first in human study EZH117208 (present study), an increase in level of ALT has been noted in the group of subjects receiving doses of 1800 mg to 3000 mg (single infusion dose). None of these ALT increases have been associated with increase in total bilirubin or INR and all have shown improvement following either withholding or discontinuing GSK2816126. The 3000 mg dose has been declared to exceed the MTD. The highest dose being explored in this study is 2400 mg .
 
In nonclinical species given GSK2816126, twice weekly for 2 and/or 4 weeks, changes in liver pathology (inflammation, hyperplasia) in dogs and clinical chemistry parameters (i.e. increases in ALT, AST, alkaline phosphatase (ALP), bilirubin and decreases in albumin) in rats and dogs were observed and were consistent with systemic inflammation. These effects were considered secondary to vascular damage at the infusion and/or surgical site and attributable to vascular or extravascular irritant (vesicant) effects of GSK2816126 and prolonged intravenous catheterization.
 
No current evidence suggests the presence of reactive metabolites. No glutathione conjugates were identified in the in vitro, ex vivo studies that were
	Dosing at 3000 mg has been discontinued, with the highest dose being explored is at 2400 mg. Continued laboratory and clinical monitoring for liver dysfunction (LFT, coagulation parameters INR/PTT, other blood chemistry, clinical observation for jaundice). Dose management and stopping criteria as per guidelines for non-hematologic toxicity (Section 3.8.3 and Table 4) and hepatic safety monitoring (Section 8.3.1)

Potential Risk of Clinical Significance	Data/Rationale for Risk	Mitigation Strategy

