6.3. Permanent Discontinuation from Study Treatment

Subjects will receive study treatment until disease progression, death or unacceptable toxicity, including meeting stopping criteria for liver chemistry defined in Section [8.3.1](#). In addition, study treatment will be permanently discontinued for any of the following reasons:

- Substantial deviation(s) from the protocol
- Request of the subject or proxy (withdrawal of consent by subject or proxy)
- Investigator's discretion
- A dose delay of >21days unless the investigator and GSK Medical Monitor agree that further treatment may benefit the subject
- Intercurrent illness that prevents further administration of study treatment(s)
- Subject is lost to follow-up
- Study is closed or terminated
- Female subject who becomes pregnant while on study treatment

The primary reason study treatment was permanently discontinued must be documented in the subject's medical records and eCRF.

If the subject voluntarily discontinues from treatment due to toxicity, 'adverse event' will be recorded as the primary reason for permanently discontinuation on the eCRF.

Once a subject has permanently discontinued from study treatment, the subject will not be allowed to be retreated.

All subjects who discontinue from study treatment will have safety/disease assessments at the post study treatment Follow Up Visit as specified in the Time and Events Tables.

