8.3.1.1. Study Treatment Restart or Rechallenge

If subject meets liver chemistry stopping criteria do not restart/rechallenge subject with study treatment unless:

- GSK Medical Governance approval **is granted**
- Ethics and/or Institutional Review Board (IRB) approval is obtained, if required, and
- Separate consent for treatment restart/rechallenge is signed by the subject

Refer to [Appendix 3](#) for full guidance

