
 • Immediately discontinue study treatment • Report the event to GSK within 24 hours • Complete the liver event eCRF and complete an SAE data collection tool if the event also meets the criteria for an SAE² • Perform liver event follow up assessments • Monitor the subject until liver chemistries resolve, stabilize, or return to within baseline (see MONITORING below) • Do not restart/rechallenge subject with study treatment unless allowed per protocol and GSK Medical Governance approval is granted (refer to Appendix 3) • If restart/rechallenge is not granted, permanently discontinue study treatment and may continue subject in the study for any protocol specified follow up assessments 	
 • Viral hepatitis serology⁴ • Blood sample for pharmacokinetic (PK) analysis, obtained approximately 48 h after last dose⁵ • Serum creatine phosphokinase (CPK) and lactate dehydrogenase (LDH). • Fractionate bilirubin, if total bilirubin\geq2xULN • Obtain complete blood count with differential to assess eosinophilia • Record the appearance or worsening of clinical symptoms of liver injury, or hypersensitivity, on the AE report form • Record use of concomitant medications on the concomitant medications report form including acetaminophen, herbal remedies, other over the counter medications • Record alcohol use on the liver event alcohol intake case report form

MONITORING:

For bilirubin or INR criteria:

- Repeat liver chemistries (include ALT, AST, alkaline phosphatase, bilirubin) and perform liver event follow up assessments within **24 hrs**
- Monitor subjects twice weekly until liver chemistries resolve, stabilize or return to within baseline
- A specialist or hepatology consultation is recommended

For All other criteria:

- Repeat liver chemistries (include ALT, AST, alkaline phosphatase, bilirubin) and perform liver event follow up assessments within **72 hrs**
- Monitor subjects weekly until liver chemistries resolve, stabilize or return to within baseline

For bilirubin or INR criteria:

- Anti-nuclear antibody, anti-smooth muscle antibody, Type 1 anti-liver kidney microsomal antibodies, and quantitative total immunoglobulin G (IgG or gamma globulins).
- Serum acetaminophen adduct high pressure liquid chromatography (HPLC) assay (quantifies potential acetaminophen contribution to liver injury in subjects with definite or likely acetaminophen use in the preceding week [[James, 2009](#)]).

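### For an ALT rise that meets a liver stopping criterion, Sections 3.8.3, 6.3 and 8.3.1/Appendix 3 give conflicting restart instructions, and the protocol does not say which governs

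*Protocol*

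**What the plan says.** Section 1.3.1 (Risk Assessment, Hepatic Toxicity) reports that in this study "an increase in level of ALT has been noted in the group of subjects receiving doses of 1800 mg to 3000 mg". It adds that none of the increases came with a rise in total bilirubin or INR, and that all improved when the drug was withheld or stopped. The mitigation column then points to two sets of rules: "Dose management and stopping criteria as per guidelines for non-hematologic toxicity (Section 3.8.3 and Table 4) and hepatic safety monitoring (Section 8.3.1").

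Those rules, and a third section, say the following.

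- **Section 3.8.3 and Table 4** cover all drug-related non-hematologic toxicity by worst grade. Grade 3 and 4 events are held for up to 2 weeks, and on recovery "treatment with GSK2816126 may be restarted at 1 dose level lower than the current dose". The text adds: "For a non-DLT, the treatment with GSK2816126 could restart at a full dose, if deemed appropriate". For an event that has not recovered by 14 days the default is withdrawal, followed by a relaxation: "However, if the investigator and GSK Medical Monitor agree that further treatment will benefit the subject, treatment can restart at 1 dose level lower".
- **Section 8.3.1.1** states: "If subject meets liver chemistry stopping criteria do not restart/rechallenge subject with study treatment unless" three conditions are met, namely GSK Medical Governance approval, ethics/IRB approval where required, and a separate signed consent. **Appendix 3 (15.3.1)** lists ALT ≥5×ULN among the stopping events for subjects who entered with ALT ≤2.5×ULN. The first required action is "Immediately discontinue study treatment". Under Appendix 3 discontinuation becomes permanent if restart or rechallenge is not granted, and after an approved restart the dose is the one GSK specifies.
- **Section 6.3**, headed as permanent discontinuation, names the Section 8.3.1 liver criteria in its opening sentence as an example of unacceptable toxicity that ends treatment. It later says: "Once a subject has permanently discontinued from study treatment, the subject will not be allowed to be retreated".

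**The concern.** Restart after a liver signal is a decision on which a site needs one answer. As written, the answer depends on which section the site opens. A site using Table 4 could resume dosing after a hold of up to two weeks without the governance approval and separate consent that Appendix 3 requires. A site using Section 6.3 could conclude that the subject is off treatment for good and never ask for the review that Appendix 3 provides.

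There is also a consequence for the data. Dose interruptions, dose reductions and withdrawals due to adverse events are among the primary Part 1 endpoints (Section 2.1) and secondary in Part 2 (Section 2.2). The same ALT event would be counted as an interruption with reduction at one site and as a withdrawal at another. These summaries feed the choice of recommended Phase 2 dose, so part of the variation in them could reflect the section followed and not tolerability.

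**Working it through.** No arithmetic applies. The check is to take one event, follow it through each section, and look for any cross-reference, exception or order of precedence that would bring the sections together.

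**Event.** A subject with entry ALT ≤2.5×ULN has a drug-related ALT ≥5×ULN that returns to Grade 1 or below within 14 days.

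| Source | Immediate action | May dosing resume? | Who must agree | Dose on resuming |
|---|---|---|---|---|
| 3.8.3/Table 4 (Grade 3–4) | Hold up to 2 weeks | Yes | No special approval stated | One level lower; full dose possible for a non-DLT |
| 8.3.1.1/Appendix 3 | Discontinue at once | Only if all conditions are met | GSK Medical Governance, ethics/IRB if required, subject by separate consent | Specified by GSK |
| 6.3 (natural reading) | Permanent discontinuation | No | No exception stated | Not applicable |

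**Does the conflict depend on the CTCAE grade of ALT ≥5×ULN?** The protocol does not print the ALT grade limits, so any mapping is an assumption. It is not needed. Table 4 leaves the dose unchanged at Grade 1, allows continued dosing or a hold at Grade 2, and prescribes hold then reduce at Grades 3 and 4. None of these rows matches immediate discontinuation with a conditional bar on restart.

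**Is there an exception or precedence rule?**

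1. Section 3.8.3 does not mention liver chemistry, Section 8.3.1 or Appendix 3. Its only cross-reference on withdrawal is to Section 6.3.
2. Section 3.9.1 asks for Medical Monitor approval to restart after 14 days of interruption. That is a different approval from Medical Governance, and it does not reach a restart inside 14 days.
3. Section 1.3.1 joins the two sets of rules with a plain conjunction and does not rank them.
4. Section 6.3 cites Section 8.3.1 for the stopping criteria but does not mention restart or rechallenge.
5. The liver algorithms in Figures 1 and 2 are not visible in the text at hand. The Appendix 3 text that gives the criteria makes no exception for Section 3.8.3.

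**Is the full-dose branch reachable?** Section 3.3.3 defines a DLT by the first 28 days, and later events count only if the investigator and Medical Monitor judge them so. In cycle 1 a clinically significant Grade 3 or higher event is normally a DLT, so the branch is largely closed. From cycle 2 on, a liver event is a non-DLT unless judged otherwise, and the branch is open.

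**Section 6.3 against Appendix 3.** Section 6.3 puts the liver criteria in the sentence that opens the permanent-discontinuation section. It introduces the remaining reasons as additional grounds for permanent discontinuation, which implies that the first group is permanent too. Appendix 3 makes a liver stopping event permanent only when restart is refused. On that reading the two do not agree.

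**The case against.** The strongest reply is that a site can satisfy everything by following the strictest applicable text. Table 4 is a guideline in permissive language, while the liver rule is a specific prohibition that appears in Section 8.3.1.1 and twice in Appendix 3. Appendix 3 also requires that a restart be both allowed by the protocol and approved by Medical Governance, so permission under Table 4 would be necessary but not sufficient. Table 4 keeps a sensible role below the stopping threshold: Appendix 3 lets a subject with ALT from 3× to below 5×ULN continue under weekly monitoring if bilirubin is below 2×ULN and there are no symptoms. This is a reasonable reconstruction and probably close to what was intended. But the protocol does not state it, and Section 1.3.1 names both sets of rules for the same toxicity. It also leaves Section 6.3 against Appendix 3 unresolved.

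A second reply is that ALT ≥5×ULN must be reported to GSK within 24 hours (Section 8.4.2 and Appendix 3), so the sponsor would know before any restart. That stands as a safeguard. It is a reporting duty, though, and does not say which dosing rule applies.

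Four stronger readings are tempting, and the protocol does not support them.

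- *A high-grade ALT rise has already occurred.* Section 1.3.1 gives no grade, and its description (no bilirubin or INR rise, all improving) does not supply one.
- *Section 6.3 expressly forbids retreatment after a liver stopping event.* Its no-retreatment sentence applies once discontinuation is permanent. That a liver event counts as permanent is inferred from the heading and the sentence structure.
- *The 13% mortality in Appendix 3 measures the risk here.* That figure is for rechallenge after drug-induced liver injury across all drugs, and Appendix 3 adds that recurrence is rare with some of them.
- *Planned enrolment gives the scale.* The 27 + 15 = 42 Part 1 expansion subjects and the 4 × 32 + 40 = 168 Part 2 subjects are planned maxima and may overlap, because Section 3.4 carries earlier subjects treated at the MTD/RP2D into the Part 2 analysis. Neither is a count of expected events.

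**Conclusion.** The point holds as a contradiction within the protocol on a matter of subject safety. For a drug-related ALT rise that meets a liver stopping criterion, Section 3.8.3/Table 4 permits a restart that Section 8.3.1.1 and Appendix 3 bar without three further steps, and Section 1.3.1 applies both without ranking them. This part rests on the text alone. The conflict between Section 6.3 and Appendix 3 rests on the natural but not the only reading of Section 6.3, and is correspondingly less certain.

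The number of subjects affected, and the effect on the tolerability summaries, cannot be estimated, because the protocol gives no rate for ALT ≥5×ULN at any dose. What can be said is that the situation is foreseeable: ALT increases were seen at 1800 to 3000 mg, and Section 1.3.1 keeps 2400 mg under exploration. No view is taken on which restart rule is right.

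**What to change.** Reconcile Sections 1.3.1, 3.8.3/Table 4, 6.3 and 8.3.1/Appendix 3.

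- In Section 3.8.3/Table 4, state whether events that meet a liver stopping criterion are covered and, if not, which section governs them.
- In Section 6.3, state how a liver stopping event relates to the Appendix 3 restart/rechallenge process, so that it is clear when discontinuation becomes permanent.
- In Section 1.3.1, make the cross-reference follow the same order.

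The sponsor chooses the rule. The cost is a line in Table 4, a clause in Section 6.3, a matching edit in Section 1.3.1 and a letter to sites. No procedure, sample size or analysis changes.

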3.3.3. Dose Limiting Toxicity

Dose-limiting toxicity (DLT): An event will be considered a DLT if it occurs within the first 4 weeks (28 days) of treatment and meets one of the following criteria (Table 3 [NCI-CTCAE, 2009]) unless it can be clearly established that the event is unrelated to treatment.

Table 3 Dose-Limiting Toxicity Criteria

Toxicity	DLT Definition
Hematologic	
 Grade 4 absolute neutrophil count (ANC) for >7 days Febrile neutropenia (according to CTCAE v.4.0 criteria) Grade 4 thrombocytopenia or anemia for >7 days
Non-hematologic	
 Grade 3 or greater nausea, vomiting, or diarrhea that does not respond to standard medical care within 48 hours Grade 3 or greater clinically significant non-hematologic toxicity per national cancer institute - common terminology criteria for adverse events (NCI-CTCAE), v 4.0
Infusion reactions	
 Infusion reactions will not be considered a DLT unless a \geqgrade 3 reaction recurs after administration of optimal prophylaxis
Other	
 Inability to receive >75% of scheduled doses in treatment period due to toxicity Grade 2 or higher toxicity that does not meet the above definitions but, in the judgment of the investigator and GSK medical monitor, is dose limiting Grade 2 or higher toxicity which occurs beyond 28 days which in the judgment of the investigator and GSK Medical Monitor is considered to be a DLT

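### Section 3.8.3 gives two restart rules for a recovered Grade 3 or 4 non-DLT event: Table 4 reduces the dose by one level, while the paragraph below it permits full dose

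*Protocol*

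**What the plan says.** Table 4 in Section 3.8.3 is a guideline for drug-related non-hematologic toxicity and works by worst grade. For Grades 3 and 4 it directs a hold of up to two weeks for recovery, "then dose reduce to 1 dose level lower per dose escalation scheme". That row has no DLT condition and offers no full-dose restart. The Grade 2 row does bring in DLT status: after listing options that keep the dose unchanged, it allows the subject to "dose reduce to 1 dose level lower per dose escalation scheme if the toxicity is considered a DLT".

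The paragraph directly under the table works by DLT status instead. For a toxicity that recovers within 14 days of stopping, "treatment with GSK2816126 may be restarted at 1 dose level lower than the current dose". It then adds: "For a non-DLT, the treatment with GSK2816126 could restart at a full dose, if deemed appropriate". Neither sentence is limited to a grade.

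Section 3.9.1 fixes the size of a reduction at one dose level and allows later re-escalation with the Medical Monitor's approval. It does not say whether a Grade 3 or 4 non-DLT calls for a reduction, or which part of Section 3.8.3 takes precedence.

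**The concern.** One section uses two different variables, grade and DLT status, to set the same quantity, the restart dose. Where a severe event is not a DLT, the two need not agree, and no order of precedence is given.

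Two things are at stake. The first is consistent handling of a subject who has just had a severe drug-related toxicity. Section 1.3.1 relies on Section 3.8.3 and Table 4, together with the hepatic monitoring rules in Section 8.3.1, as mitigation for liver toxicity. The second is what the safety summary means. Dose interruptions and reductions are listed in the Part 1 primary safety endpoint (Section 2.1) and again among the Part 2 secondary endpoints (Section 2.2). If some sites follow the table and others the paragraph, the count of reductions partly reflects which text was read rather than how well the drug was tolerated.

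**Working it through.** The point rests on no calculation in the protocol, so the check is to apply both rules to the same cases and then ask whether the conflicting case can occur.

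**Step 1. Both rules side by side, for a drug-related non-hematologic event that has recovered within 14 days of a hold.**

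| Event | Table 4 | Paragraph under Table 4 | Agree? |
|---|---|---|---|
| Grade 2, DLT | one level lower is available | one level lower | compatible |
| Grade 2, not a DLT | same dose | one level lower, or full dose | compatible through the full-dose option |
| Grade 3 or 4, DLT | one level lower | one level lower | yes |
| Grade 3 or 4, not a DLT | one level lower | one level lower, or full dose | **no** |

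Only the last row conflicts.

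**Step 2. Can a drug-related Grade 3 or 4 event fail to be a DLT?** Section 3.3.3 opens with a time window: "An event will be considered a DLT if it occurs within the first 4 weeks (28 days) of treatment" and meets a criterion in Table 3. Two routes follow.

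- *After Day 28.* A later event becomes a DLT only under the last criterion in Table 3, which covers "Grade 2 or higher toxicity which occurs beyond 28 days which in the judgment of the investigator" and the Medical Monitor counts as one. A late Grade 3 or 4 event that they do not so judge is a non-DLT.
- *Within 28 days.* One criterion is "Grade 3 or greater nausea, vomiting, or diarrhea that does not respond to standard medical care within 48 hours". An event of this kind that does respond in time falls outside that criterion. It is a non-DLT on the reading that this specific criterion, rather than the general one for clinically significant Grade 3 toxicity, is meant to decide such events, and provided it is not judged dose limiting on other grounds.

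So the conflicting case can arise.

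**Step 3. Which events leave the comparison because another rule governs them?** QTcF prolongation (Section 3.8.1), infusion reactions (Section 3.8.2) and liver chemistry events (Section 8.3.1 and Appendix 3) have their own stopping or restart rules. They are set aside here.

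**Step 4. Is there a tie-breaker?** Section 3.9.1 gives the size of a reduction and the approval needed to go back up. It gives no rule for choosing between the table and the paragraph. It also adds a contrast: returning to a higher dose after a reduction needs the Medical Monitor's approval, whereas the full-dose sentence in Section 3.8.3 names no approver.

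**The case against.** The strongest reply is that the two texts can be read together. Table 4 is titled a guideline, and the full-dose sentence is permissive and conditional. The paragraph could be a general rule (one level lower) with a discretionary exception, or the exception could be meant for Grade 2, the only row that mentions DLT status. It might also be aimed at events clearly unrelated to treatment, which cannot be DLTs and to which Table 4 does not apply.

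Part of this stands. Because the wording is permissive, a subject can receive a different dose under the two texts; it does not follow that any subject will. Unrelated events raise no conflict. The Grade 2 reading is weaker. The Grade 2 row already allows the same dose, so the sentence would add nothing there. The next paragraph, on toxicity that has not resolved by 14 days, parallels the Grade 3 and 4 row. No limit to Grade 2 or to unrelated events is written down.

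A second reply is that Section 3.9.1 already foresees a return to a higher dose. That narrows the practical gap to timing and approval, but leaves the immediate restart dose unsettled.

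A reader might also infer that all, or nearly all, Grade 3 or 4 events after Day 28 are affected. The protocol does not support that: late events can be judged DLTs, and the QTcF, infusion-reaction and liver rules remove others. Nor does a share of treatment time measure the problem. With n cycles of 28 days, the share after the DLT window is (n − 1)/n: 1/2 = 50% for two cycles and 5/6 = 83% for six. The protocol sets no number of cycles, so n is an assumption, and a share of time is not a share of events.

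**Conclusion.** The inconsistency is real and confined to one class: drug-related Grade 3 or 4 non-hematologic events that are not DLTs, recover within 14 days and have no rule of their own. For these, Table 4 leads to one dose level lower, while the paragraph under it allows either that or full dose. The conclusion rests on reading the full-dose sentence as written, without an unstated limit on grade.

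The protocol gives no rate for such events, so neither the number of subjects affected nor the effect on the dose-reduction summary can be stated.

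A reader might go on to infer that the choice of the recommended Phase 2 dose is compromised. The protocol does not show that. The MTD rule in Section 3.3.4 rests on DLT counts, which the restart dose after a non-DLT does not alter. The safety profile also informs the recommended dose, but no route from the restart dose to that decision is set out. What is supported is narrower: inconsistent handling after severe toxicity is possible, and with it a less interpretable count of dose reductions within a listed primary safety endpoint. That justifies a correction. Which restart rule is clinically right is for the sponsor to decide, and no view is taken here.

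**What to change.** The sponsor must reconcile the Grade 3 and 4 row of Table 4 with the paragraph below it. The revised section should state whether grade or DLT status governs the restart dose after a Grade 3 or 4 event, and should carry the same wording in the table and the text.

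The cost is amendment wording only; the change needs no new assessments, sample-size work or analysis method.
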